8.1.3 Adverse Events

An adverse event (AE) is any unfavorable, harmful, or pathologic change in a research subject as indicated by physical signs, symptoms and/or clinically significant laboratory abnormalities that occurs in association with the use of a product (trial-related), whether or not considered to be product-related. This includes intercurrent illnesses, injuries, worsening of pre-existing conditions, and events occurring as a result of product abuse or overdose. Stable pre-existing conditions and/or elective procedures are not adverse events.

Adverse events are captured after all screening procedures are completed and subject receives the initial dose of investigational product on Day 0. All events fulfilling any part of the AE definition must be recorded on the Adverse Event CRF (with the exception of pre-defined immediate complaints or symptoms/signs of vaccine reactogenicity in the first seven (7) days following immunization, which are captured on other specific instruments; see above) and graded according to the Adverse Event and Clinical Laboratory Grading tables in **Appendix B**.

Treatments and procedures are not adverse events; rather, the illness which

precipitates them should be recorded. For example, “cholecystectomy”, is not an AE, but the diagnosis of “cholecystitis” or “gall stones” leading to the surgical (or medical) treatment is an AE. Where possible, specific diagnoses are preferred in reporting AEs. Individual complaints or findings may be reported as AEs, but when multiple complaints or findings occur together and can be logically and defensibly assembled into a single clinical syndrome or diagnosis, the latter is preferred. For example, an isolated finding of elevated AST and ALT would be recorded as “elevated transaminases.”

8.1.4 Clinical Laboratory Findings as Adverse Events

Clinical laboratory measures, except for urine pregnancy tests, are not required by the protocol. It is possible that laboratory tests could be ordered to assess an adverse event. Clinical laboratory abnormalities may be adverse events in themselves, and should be reported as adverse events if they raise clinical concern or are sufficient to initiate additional diagnostic tests. Clinical laboratory abnormalities that form part of a coherent clinical syndrome (e.g., transaminase elevations in well-defined hepatitis as described in **8.1.3** above) need not be listed as separate adverse events so long as the syndrome of which they are components is captured (e.g., it is not necessary to capture “hepatitis” and “elevated hepatic transaminases” and “anorexia” separately – the first of these includes the latter two). Clinical laboratory abnormalities that are reported as adverse events should be followed to resolution or until stable, and ancillary case report forms will be provided to capture these data. Subjects with persistent abnormalities will then be referred to their local physician for any unresolved issues.

Severity of Event: All AEs will be assessed by the clinician using a protocol defined grading system (see **Appendix B**). For events not included in the protocol grading system, the following guidelines will be used to quantify intensity.

- Mild: events require minimal or no treatment and do not interfere with the patient’s daily activities.
- Moderate: events result in a low level of inconvenience or concern with the therapeutic measures. Moderate events may cause some interference with functioning.
- Severe: events interrupt a patient’s usual daily activity and may require systemic drug therapy or other treatment. Severe events are usually incapacitating.
- Life threatening: any adverse drug experience that places the patient or subject, in the view of the investigator, at immediate risk of death from the reaction as it occurred, i.e., it does not include a reaction that had it occurred in a more severe form, might have caused death.

Changes in the severity of an AE should be documented to allow an assessment of the duration of the event at each level of intensity to be performed. Adverse events characterized as intermittent require documentation of onset and duration of each episode.

Relationship to Study Products: The clinician's assessment of an AE's relationship to test article is part of the documentation process, but it is not a factor in determining what is or is not reported in the study. If there is any doubt as to whether a clinical observation is an AE, the event should be reported. All AEs must have their relationship to study product assessed. In a clinical trial, the study product must always be suspect. To help assess, the following guidelines are used.

- **Unrelated:** The adverse event is clearly not related to the Investigational Product(s). This category applies to those adverse events, which, after careful consideration are clearly due to extraneous causes.
- **Possibly:** The adverse event may be related to the Investigational Product(s). This category applies when there is modest suspicion that the experience may be related to study medication, but there is also suspicion that other etiologies (e.g. concomitant illness or medication, etc.) are also possible.
- **Probably:** The adverse event is likely related to the Investigational Product(s). This category applies when the experience most likely seems to be related to the study medication but there is a modest suspicion that it could be related to other causes.
- **Definitely:** The adverse event is clearly related to the Investigational Product(s). This category applies when after careful medical consideration there is almost no consideration of other causation.

8.1.5 Double Reporting of Reactogenicity Findings/Complaints

As per sections 8.1.1, and 8.1.2 above, findings and/or complaints specifically captured by the Memory Aid should NOT, in general, be additionally recorded as AEs if they occur within seven (7) days of a study vaccine dose.

The rationale for not doubly-reporting reactogenicity events as AEs is as follows. The specified range of reactogenicity complaints and findings are those reasonably expected to be associated with IM influenza vaccine. These data are collected by clinical study team member(s) and transferred to CRFs, analyzed, and reported in detail to investigators and regulatory authorities as *vaccine reactions* and are *presumed to be product-related*. Separation of these numerically frequent, but usually minor, vaccine reactions from other classes of adverse events has two benefits to the safety analysis. It markedly simplifies the careful analysis of the frequency and duration of these reactions and their comparison among treatment groups. In addition, these reports would, if reported as routine AEs, tend to cluster in a few MedDRA body systems. Separating these common, expected vaccine reactions from other AEs allows for the elucidation of other potentially important, but less common, types of events in the statistical analysis of AEs in those body systems.

There are *three exceptions* to the rule regarding double reporting:

- a) Any of these findings or complaints which fulfills the definition of “Serious Adverse Event” (see **Section 8.2**) should be recorded as an AE (and reported as per **Section 8.3**),
- b) Any of these findings or complaints that persists beyond seven (7) days after a study vaccine dose should be recorded as an AE,
- c) Any of these findings or complaints which the investigator *unequivocally* categorizes, based on strong clinical evidence, as unrelated to the test article should be recorded as an AE. In this case the investigator *must* assign a causality of “unrelated” (not “unknown”) and record a clear rationale in source documents.

If a reactogenicity finding or complaint is doubly-recorded as an AE, site personnel should take care to record a verbatim AE identical to the wording of the reactogenicity finding/complaint, and also an AE start date identical to the onset date implied by the reactogenicity case report forms. The sponsor will then report such events as both reactogenicity and AE findings, but will be able to link the two reports in the database for discussion and analysis purposes.

8.2 Definition of Serious Adverse Events

A serious adverse event (SAE) is any adverse event that results in any of the following outcomes:

- a) death,
- b) an immediate threat to life,
- c) inpatient hospitalization or prolongation of an existing hospitalization,
- d) persistent or significant disability/incapacity, or
- e) a congenital anomaly/birth defect.

Important medical events that do not result in one of these outcomes, but, based on appropriate medical judgment, are deemed to jeopardize the subject or require medical or surgical intervention to avert one of the listed outcomes, may also be considered SAEs at the investigator’s discretion.

8.3 SAE Reporting Procedures

8.3.1 SAE Detection and Reporting

Any AE considered serious by the PI or Subinvestigator or which meets the aforementioned criteria must be submitted on an SAE form to Vaxinnate Corporation by to the email or fax listed below. Questions about SAE reporting can also be referred to [name] using the same contact information.

[name]
Email: [contact] or his designee
[name] Email: [contact]

VaxInnate Corporation
[name]
[name]
[contact] cellular [contact] or [contact]
[name] [contact]

The study clinician will complete a Serious Adverse Event Form within the following timelines:

- All deaths and immediately life-threatening events, whether related or unrelated, will be recorded on the Serious Adverse Event Form and sent by fax within 24 hours of site awareness.
- Serious adverse events other than death and immediately life-threatening events, regardless of relationship, will be reported via fax by the site within 72 hours of becoming aware of the event.

All SAEs will be followed until satisfactory resolution.

All SAEs must also be reported by the PI as soon as possible to the institutional review board reviewing and approving the clinical trial. It is the responsibility of VaxInnate to report the event as specified in 21 CFR Part 312.32: fatal and life-threatening events within 7 calendar days (by phone or fax) and all other SAEs in writing within 15 calendar days. All serious events designed as “unrelated” to study product(s), will be reported to the FDA at least annually in a summary format.

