4 STUDY POPULATION

4.1 Number of Subjects

Eighty (80) healthy adult subjects will be recruited for enrollment at two study centers into one of two groups.

Group A is comprised 40 subjects receiving a standard dose of TIV IM first followed by 1 µg VAX102 IM.

Group B is comprised 40 subjects receiving a standard dose of TIV IM first followed by F105 (Placebo) IM.

The investigators will make a reasonable attempt to screen enough subjects to meet the enrollment for each group. Once the subject has received study vaccination on Day 0, subjects will not be replaced.

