4.7 Halting Rules

- If one or more subjects experience a clinically significant AE or laboratory abnormality (Grade 3 or 4), there will be no further enrollment until a full safety review is performed.
- The study will be halted (no new enrollments and no further investigational product administered) if one of the following occurs:
 - a. One subject experiences a serious adverse event (SAE) assessed as possible, probably or definitely related to investigational product or
 - b. There is a subject death assessed as possibly, probably or definitely related to investigational product.

A safety monitoring committee (SMC) comprised of a Principal Investigator from each site, VaxInnate, and an Independent Safety Monitor, will be set-up to assess in a blinded fashion the safety and reactogenicity should one of the above halting rules be met. The Independent Safety Monitor may be unblinded to study treatment, as needed, to adequately assess safety issues.

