8.4 Halting Rules

- If one or more subjects experience a clinically significant AE or laboratory abnormality (Grade 3 or 4), there will be no further enrollment until a full safety review is performed.
- The study will be halted (no new enrollments and no further investigational product administered) if one of the following occurs:
 - c. One subject experiences a serious adverse event (SAE) assessed as possible, probably or definitely related to investigational product or
 - d. There is a subject death assessed as possibly, probably or definitely related to investigational product.

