8.5 Safety Oversight

VaxInnate will serve as the Sponsor for this study. Sponsor responsibilities will include the creation and oversight of the protocol development, submission of the Investigational New Drug (IND) application to the Food and Drug Administration (FDA), monitoring and ensuring Good Clinical Practice (GCP) conduct of the study, and the submission of annual and final study reports to the FDA.

If there appears to be a safety issue which would cause the halting of the trial, the site will alert VaxInnate and inform them of their findings.

A safety monitoring committee (SMC) comprised of a Principal Investigator from each site, VaxInnate, and an Independent Safety Monitor, will be set-up to assess in a blinded fashion the safety and reactogenicity should one of the above halting rules be met. The Independent Safety Monitor may be unblinded to study treatment, as needed, to adequately assess safety issues.

If the trial is halted or amendments are recommended, the sites' IRBs, and FDA will be notified.

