10.5 Institutional Review Board

The Investigator must submit the final protocol and proposed informed consent document to an Institutional Review Board (IRB) that is constituted and operates in accordance with Part 56 of Title 21 of the Code of Federal Regulations. The IRB will provide the Investigator with a written decision regarding the conduct of the study at that site and a copy of the document will be forwarded to the Project Manager. The study will not be initiated and no subjects will be enrolled until the appropriate documentation of IRB approval of the study protocol and the informed consent has been received.

Substantive modifications to the protocol will be submitted to the IRB for approval. These modifications may be implemented only after IRB written approval has been received and forwarded to the Project Manager. Administrative changes to the protocol such as a change that has no effect on the conduct of the study or risk to the subject should be submitted to the IRB for review, but formal approval is not required.

The Investigator must also submit any other written information that will be given to the study subjects as well as any advertisements for subject recruitment, if used, to the IRB for approval prior to implementing these documents.

The Investigator will make appropriate and timely reports to the IRB as required by applicable government regulations and IRB policy. In addition to progress reports, all known information regarding serious and unexpected adverse events, whether observed at their clinical site or at another site participating in a clinical investigation with the study product, will be reported to the IRB. It is the Sponsor and/or its representative's responsibility to inform the Investigator of serious and unexpected events observed at other investigational sites.

It is the Investigator's obligation to provide the Sponsor and/or its representatives with copies of all study-related correspondence with the IRB in a timely fashion and to retain originals in a file. This IRB correspondence file will be made available as requested to appropriate representatives for monitoring or quality assurance review and to FDA representatives during site audits.

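### One related SAE halts the whole study, yet a related SAE that is neither fatal nor immediately life-threatening may be reported up to 72 hours after awareness, and the separate alert duties carry no deadline

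*Protocol*

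**What the plan says.** Protocol sections 4.7 and 8.4 carry the same halting rule: "The study will be halted (no new enrollments and no further investigational product administered) if one of the following occurs", the first listed condition being "One subject experiences a serious adverse event (SAE) assessed as possible, probably or definitely related to investigational product". The rule applies to the study as a whole, and section 4.1 describes two centres: "Eighty (80) healthy adult subjects will be recruited for enrollment at two study centers into one of two groups".

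Section 8.3.1 governs SAE reporting by the site: "The study clinician will complete a Serious Adverse Event Form within the following timelines". Deaths and immediately life-threatening events, related or not, have 24 hours from site awareness. For the rest, "Serious adverse events other than death and immediately life-threatening events, regardless of relationship, will be reported via fax by the site within 72 hours" of awareness.

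Two other duties bear on the speed of a halt. Section 8.5: "If there appears to be a safety issue which would cause the halting of the trial, the site will alert VaxInnate". Section 10.5 makes it the sponsor's "responsibility to inform the Investigator of serious and unexpected events observed at other investigational sites". Neither gives a time. Under 8.5 the safety monitoring committee, which includes a Principal Investigator from each site, "will be set-up to assess in a blinded fashion the safety and reactogenicity should one of the above halting rules be met".

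There is also a pause rule. A clinically significant Grade 3 or 4 event or laboratory abnormality stops enrolment until a full safety review, with no judgement of relatedness. In the general illness row of Appendix B, hospitalisation is Grade 4.

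**The concern.** The halting rule turns on relatedness; the reporting clock turns on outcome. The event most likely to sit between the two is a hospitalisation judged possibly related but not immediately life-threatening. It meets the halting rule, yet falls in the slower reporting class, the same 72 hours that 8.3.2 allows for notice of a pregnancy.

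Each subject is dosed once, on Day 0. Anyone dosed at the other site before word arrives is therefore a newly exposed healthy volunteer, and the rule exists to prevent exactly that exposure. The reporting site is bound by 4.7 and can stop at once. The other site can act only when it is told.

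**Working it through.** **Step 1. Trigger against clock.** There is no figure in the protocol to reproduce, so the rules are set side by side.

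| Event | Effect under 4.7/8.4 | Site-to-sponsor limit in 8.3.1 |
|---|---|---|
| Death, unrelated | Not a halt | 24 h |
| Death or immediately life-threatening SAE, at least possibly related | Halt | 24 h |
| Hospitalisation without immediate threat to life, at least possibly related | Halt | 72 h |
| Same hospitalisation, unrelated | Not a halt (may pause) | 72 h |

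The third row is the gap.

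**Step 2. Does another provision supply a deadline?**
- 8.5 alert by the site: no time stated.
- 10.5 notice to other investigators: no time stated.
- Prompt reporting in 8.3.1 to the IRB, and the sponsor's 7- and 15-day reports: these go to the IRB and the FDA, not between site and sponsor or between sites.
- Pause rule: no notification time.
- Committee: convened once a halting rule is met, with no time for convening it.
- Frequent telephone contacts under 10.8: a monitoring method, not a deadline.

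So 72 hours is the only stated site-to-sponsor limit for this event, and none is stated for telling the other site.

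**Step 3. Length of the window.** The 72 hours run from awareness; the halt condition is met on assessment of relatedness. Let *a* be the hours from awareness to that assessment. If the site uses the full limit, the time left after the condition is met is 72 − *a* under the present text and 24 − *a* (or zero, if *a* exceeds 24) under a 24-hour limit. The difference is 48 hours when *a* ≤ 24, and 72 − *a* when *a* lies between 24 and 72. The gain is thus at most 48 hours. Sponsor handling time is added equally in both cases and cancels from the difference.

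**Step 4. Illustration of size.** From the protocol: 80 subjects, two sites, 1:1 allocation. Assumed: 40 per site, even accrual, calendar-day average, and an enrolment period of 2 to 8 weeks. The synopsis gives a total duration of about 8 weeks, but that does not settle accrual: up to 30 days of screening plus 28 days of follow-up is already 58 days for one subject.

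Dosings at the other site = (40 / enrolment days) × (hours / 24).

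| Enrolment | Rate per site per day | 72 h | 24 h | Difference (48 h) | Of these, VAX102 (half) |
|---|---|---|---|---|---|
| 2 weeks | 40/14 = 2.86 | 8.6 | 2.9 | 5.7 | 2.9 |
| 4 weeks | 40/28 = 1.43 | 4.3 | 1.4 | 2.9 | 1.4 |
| 8 weeks | 40/56 = 0.71 | 2.1 | 0.7 | 1.4 | 0.7 |

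If subjects are dosed only on weekdays and the window falls wholly on weekdays, multiply by 7/5: the difference becomes 8.0, 4.0 and 2.0. Each day of sponsor handling adds 0.7 to 2.9 calendar-average dosings under either limit.

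**The case against.** The strongest reply is that there are two channels and no contradiction. The 72 hours govern the SAE form. The halt runs through 8.5, which is anticipatory: the site must alert the sponsor when a halting issue appears to exist, without waiting for the form or for relatedness to be settled. Section 8.3.1 lists telephone contacts as well as email and fax. The other site's Principal Investigator sits on the safety monitoring committee. A clinically significant hospitalisation would also meet the Grade 3/4 pause rule, and because subjects count as enrolled when they receive test article (6.2.1), pausing enrolment stops dosing.

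All of this stands, and it limits the point. A reader might infer that the protocol lets dosing continue for 72 hours after a halt condition is met. The text does not say that; nothing authorises a site to hold back the 8.5 alert. A reader might also take the full 72-hour column, about 2 to 9 dosings, as the harm. That counts doses given before relatedness was assessed, and those a 24-hour limit would not prevent.

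It is also fair that the 18 subjects given 1 µg in the earlier studies (Table 2) had no severe local or systemic reactions, so nothing suggests that a related SAE is likely, although 18 subjects are too few to exclude one.

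What the reply does not supply is a time. The alert, the committee and the pause rule all depend on word reaching the sponsor and then the other site, and for this class of event the only limit written down is 72 hours.

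**Conclusion.** The point holds as a timing gap in the protocol. One at-least-possibly-related SAE halts the study, but unless it is fatal or immediately life-threatening its only stated site-to-sponsor limit is 72 hours, and no limit is stated for telling the other site. Other provisions narrow the gap without putting a time on it.

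Its size is illustrative. No accrual rate or site split is stated, so the number exposed cannot be derived. With even accrual over 2 to 8 weeks at two equal sites, a 24-hour limit instead of 72 would spare at most about 1 to 6 dosings at the other site on a calendar-day average, half of them VAX102. That maximum requires the site to use its full limit, relatedness to be assessed within 24 hours, no earlier alert, and dosing to continue at the other site throughout. All of it is conditional on such an SAE occurring.

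No endpoint or analysis is affected. The change is still worth making, because it concerns exposure of healthy volunteers and costs little.

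**What to change.** In 8.3.1, place any SAE assessed as at least possibly related to product under the existing 24-hour limit; applying 24 hours to all SAEs is simpler and would also serve. In 8.5, require the site to alert the sponsor immediately, and within 24 hours at most, when a halting rule is met or appears to be met, and require the sponsor to notify the other site the same day.

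Leave the halting and pausing criteria unchanged. Do not extend the 24-hour SAE limit, or a duty to stop dosing, to every event that might meet the pause rule. That would reach isolated Grade 3 findings, such as a systolic pressure above 155 mm Hg or a haemoglobin fall of 2.1 g/dL, and would in effect move the trigger from assessed to suspected.

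The cost is two or three sentences in an amendment and slightly tighter site reporting. No subjects, visits or procedures are added.
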